**Table 14 Decision Making Criteria for Futility Analysis**

Number of Evaluable Subjects	≤ This Number of Responses to Stop Early for Futility	Probability of continuing enrolling when ORR=0.4	Probability of continuing enrolling when ORR=0.6
10	2	83.3%	98.8%
11	2	83.3%	98.8%
12	3	75.5%	98.1%
13	3	75.5%	98.1%
14	4	68.6%	97.5%
15	4	68.6%	97.5%
16	5	62.3%	96.9%
17	6	52.9%	95.7%
18	6	52.9%	95.7%
19	7	46.7%	94.9%
20	7	46.7%	94.9%
21	8	41.6%	94.2%
22	9	34.6%	92.8%
23	9	34.6%	92.8%
24	10	30.2%	91.9%
25	11	24.4%	90.2%
26	12	18.8%	87.7%
27	13	13.9%	84.5%

Number of Evaluable Subjects	≤ This Number of Responses to Stop Early for Futility	Probability of continuing enrolling when ORR=0.4	Probability of continuing enrolling when ORR=0.6
28	14	0.0%	0.0%

## 9.6. Primary Analysis

Primary analysis will be conducted approximately 15 months from the last subject first visit (LSFV). If meaningful response rate (ORR) cannot be achieved, participants may discontinue the study treatment and will undergo end of treatment and follow-up assessments as defined in Section 4.2.2. Statistical considerations and data analysis may be performed separately and/or combined for Part 1 and Part 2.

## 9.7. Final Analysis

Final analysis of the data captured in Part 1 and Part 2 will be undertaken at the end of study (Section 5.5.2). Data from the two parts may be combined for some analyses at the end of the trial, as appropriate.

## 9.8. Key Elements of Analysis Plan

Data will be listed and summarized according to GSK reporting standards, where applicable. Complete details will be documented in the RAP. Any deviations from, or additions to the original analysis plan described in this protocol will be documented in the RAP and final study report.

As it is anticipated that accrual will be spread thinly across centers and summaries of data by center would be unlikely to be informative, data from all participating centers will be pooled prior to analysis.

All data up to the time of study completion/withdrawal from study will be included in the analysis, regardless of duration of treatment.

As the duration of treatment for a given subject will depend on efficacy and tolerability, the duration of follow-up will vary between subjects. Consequently, there will be no imputation for missing data.

Demographic and baseline characteristics will be summarized.

### 9.8.1. Clinical Activity Analyses

The primary endpoint ORR and other applicable secondary endpoints (e.g., CBR, DoR, TTR, TTP, PFS) will be based on the responses assessed by the investigator.

At futility interim and the primary analysis, the primary endpoint (ORR) will be analyzed based on the All Evaluable population. Otherwise, all efficacy endpoints will be analyzed based on the All Treated population unless otherwise specified. The analytical methods planned for each endpoint are described in [Table 15](#).

**Table 15 Statistical Analysis Methods for Clinical Activity Endpoints (Part 2)**

Endpoint	Statistical Analysis Methods
Primary	
Overall Response Rate (ORR) is defined as the percentage of subjects with a confirmed PR or better (i.e. PR, VGPR, CR and sCR), according to the International Myeloma Working Group (IMWG) Response Criteria.
 
The number and percentage of subjects in the following response categories will be presented: sCR, CR, VGPR, PR, overall response (sCR+CR+VGPR+PR), minimal response (MR), stable disease (SD), progressive disease (PD), and not evaluable (NE). The corresponding 95% CI for ORR will also be provided. Subjects with unknown or missing responses will be treated as non-responders, i.e., these subjects will be included in the denominator when calculating percentages of response.

Secondary	
Secondary clinical activity endpoints of Part 2 of this study are CBR, DoR, TTR, PFS, TTP and MRD Negative Rate.
 
Clinical benefit rate (CBR), defined as the percentage of subjects with a confirmed minimal response (MR) or better per IMWG.
 
Duration of response (DoR) is defined as the time from first documented evidence of PR or better until disease progression (PD) per IMWG, or death due to PD among subjects who achieve an overall response (i.e. confirmed PR or VGPR or CR or sCR). Responders without disease progression will be censored at the censoring time point for TTP.
 
Time to response (TTR) is defined as the time between the date of first dose and the first documented evidence of response (PR or better) for subjects who achieve an overall response (i.e. confirmed PR or VGPR or CR or sCR).
 
Time to best response, defined as the time between the date of first dose and the first best documented response (PR or better) for subjects who achieve an overall response (i.e. confirmed PR or VGPR or CR or sCR).
 
Progression-free survival (PFS) is defined as the time from first dose until the earliest date of disease progression (PD) per IMWG, or death due to any cause. Determination of dates of PFS event and dates for censoring will be described in the RAP.
 
Time to disease progression (TTP) is defined as the time from first dose until the earliest date of PD per IMWG, or death due to PD. Determination of dates of TTP event and dates for censoring will be described in the RAP.
 
For all the TTE endpoints described above, median TTE with 95% CI will be estimated employing the Kaplan-Meier method. A Kaplan-Meier survival curve will be generated. The number and percentage of subjects who had the event or were censored will also be reported. In addition, PFS rate with 95% CI at 6, 12 and 18 months will be estimated using Kaplan-Meier methods for the PFS endpoint.
 
OS is defined as the time from first dose until death due to any cause. Subjects who withdraw consent from the study or are lost to follow-up will be censored at the time of withdrawal or lost to follow-up. Subjects who are still alive at the clinical cut-off date for the analysis will be censored at the last known alive date or last contact date. The last contact date will be determined by the maximum collection/assessment date from

Endpoint	Statistical Analysis Methods
	among selected data domains within the clinical database. Survival rate 12, 18 and 24 months will be reported from Kaplan-Meier analysis as data permits. .

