## 2. INTRODUCTION

### 2.1. Study Rationale

Multiple myeloma (MM) is an incurable malignancy and accounts for 1% of all cancers and for 10% of all hematologic malignancies. Worldwide, approximately 103,000 new cases are diagnosed annually, and an estimated 30,330 new cases and 12,650 deaths will occur in the U.S. in 2016 [Siegel, 2016]. Despite significant advances with current novel therapies and hematopoietic stem cell transplantation (HSCT), novel therapies like second- and third-generation proteasome inhibitors (PIs), immunomodulatory agents, and recent addition of monoclonal antibodies (mAbs), most MM patients will relapse and ultimately develop resistance to existing therapies [Laubach, 2014]. Thus, there is a need to develop treatments with novel mode of action (MOA) which could potentially prevent the cross resistance to existing therapies.

Before the introduction of daratumumab, patients with disease refractory to both immunomodulatory agents and PIs had a median overall survival (OS) ranging from 9 months [Kumar, 2012] to 12 months [San Miguel, 2013].

Daratumumab [DARZALEX, 2017], is a human IgGk monoclonal antibody that was granted accelerated approval as monotherapy for the treatment of relapsed/refractory multiple myeloma (RRMM) in the US in November 2015 based on the results from a Phase II monotherapy study (n=106), which reported 29.2% overall response rate (ORR) and median progression free survival (mPFS) of 3.7 months in patients with RRMM [Lonial, 2016]. The median number of prior lines of treatment reported in this study was 5.

Daratumumab has also been approved in combination with lenalidomide/dexamethasone or bortezomib/dexamethasone for patients who were previously treated with at least one prior line of therapy, and in combination with pomalidomide and dexamethasone for patients previously treated with at least 2 prior lines of therapy based on improvement in mPFS and ORR [DARZALEX, 2017; Janssen-Cilag International NV, 2016].

While the data with daratumumab indicates that prolongation of PFS can be achieved, patients continue to relapse after treatment with daratumumab; additional treatment options to control the disease are needed. Patients with RRMM who relapse after daratumumab, IMiD, and PI based therapies, have few treatment options available.

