- In cases where the subject is deemed 'lost to follow up', the investigator or designee must make every effort to regain contact with the subject (where possible, 3

telephone calls and if necessary a certified letter to the subject's last known mailing address or local equivalent methods). These contact attempts should be documented in the subject's medical record.

- Should the subject continue to be unreachable, only then will he/she be considered to have withdrawn from the study with a primary reason of "Lost to Follow-up".

A subject may withdraw from study treatment at any time at his/her own request, or may be withdrawn at any time at the discretion of the investigator for safety, behavioural or administrative reasons. If a subject withdraws from the study, he/she may request destruction of any samples taken, and the investigator must document this in the site study records.

[figure not shown]

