**5.5. Subject and study Completion****5.5.1. Subject completion**

For Part 1 and Part 2, a subject is considered to have completed the study if they received at least 1 cycle of combination study treatment, and:

- The subject is followed until death, or
- The subject is followed until the end of study

The end of study is defined in Section [5.5.2](#). The end of study analyses will be performed at that time.

The eCRF should continue to be completed during the follow up period (every 3 months ( $\pm 7$  days) until the end of study. Please refer to [Table 10](#) for assessments to be completed during PFS follow-up visits or OS follow-up. OS follow-up data can be based on contacting subjects via phone calls/e-mails/or, other means of communication. Subjects who cannot be contacted will be considered lost to follow up. Follow-up data will be entered into the eCRF.

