Spot Urine (albumin / creatinine ratio) 	X			
 
1. All assessments will apply to Part 1 and 2 unless stated otherwise.
 
2. Safety follow up to occur within 30 days from the last dose, or prior to the new anti-MM treatment (whichever occurs first).
 
3. PFS follow-up every 21 days (<math>\pm 7</math> days) for subjects who discontinue IP for a reason other than PD. Disease evaluations will continue until confirmed PD, death, start of a new anticancer treatment, withdrawal of consent, or end of the study whichever occurs first. Once subject progresses, move to OS Follow-up.
 
4. The survival for MM will be documented in medical charts. No visit necessary. Contacts will be made via phone calls, emails or other means of communications every 12 weeks (<math>\pm 14</math> days) until end of study (Section 5.5.2). Subject does not need to come in for visit unless they are being followed for corneal signs that are present at the end of study treatment.
 
5. AE/SAEs will be collected to 45 days post the last dose. All related SAEs are to be collected from first dose through OS follow-up. AEs/SAEs will be followed until the event is resolved, stabilized, otherwise explained or subject is lost to follow up.
 
6. If a subject develops signs / symptoms, or they require additional treatment, e.g. topical steroid for more than 7 days, additional assessment by an ophthalmologist (or optometrist, if ophthalmologist is not available) will be implemented. Intraocular pressure should be monitored if steroid eye drops are used more than 7 days. See Section 7.3.5 for list of exams.
 
7. Subjects with decreased visual acuity or corneal signs or symptoms at the end of study treatment visit will have follow-up ophthalmic exams at 3 and 6 weeks from the last dose of study treatment and then every 6 weeks (<math>\pm 7</math> days) until deemed clinically stable by an eye care professional, or up until 1 year (whichever comes first). See Section 7.3.5 for list of exams.
 
8. Perform only in women of child-bearing potential. May be either serum or urine.
 
9. Final pregnancy test (serum or urine) must be performed in women of childbearing potential at the EOT Visit. Follow up pregnancy assessment by telephone (for WOCBP only) should be performed 4 months after the last dose of belantamab mafodotin.
 
10. eGFR as calculated by Modified Diet in Renal Disease (MDRD) formula (Appendix 3)
 
11. Albumin / creatinine ratios (spot urine from first void).
 

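### Overall survival for subjects lost to follow-up is censored when they are lost, not when last known alive, which biases the Kaplan-Meier OS rates slightly upward

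*Protocol*

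**What the plan says.** Section 9.8.1, Table 15 of the protocol fixes the OS censoring dates in two consecutive sentences. Subjects who withdraw consent or are lost to follow-up "will be censored at the time of withdrawal or lost to follow-up". Subjects still alive at the clinical cut-off "will be censored at the last known alive date or last contact date", and the table goes on to say how the last contact date is derived from the clinical database. The OS output is defined as follows: "Survival rate 12, 18 and 24 months will be reported from Kaplan-Meier analysis as data permits".

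Three other places determine when a subject counts as lost:

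- Section 5.4 requires repeated attempts to regain contact (three telephone calls where possible, then if necessary a certified letter) and adds: "Should the subject continue to be unreachable, only then will he/she be considered to have withdrawn from the study", with loss to follow-up as the reason.
- Section 5.5.1, on OS follow-up: "Subjects who cannot be contacted will be considered lost to follow up".
- Table 10, note 4, on OS follow-up: "Contacts will be made via phone calls, emails or other means of communications every 12 weeks", with a window of ±14 days.

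For PFS the same table defers the matter: "Determination of dates of PFS event and dates for censoring will be described in the RAP". TTP is treated likewise. OS is not deferred.

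**The concern.** Being lost is a status assigned after contact has failed. The last date on which the subject was known to be alive is the last successful contact, which is earlier. If the subject is censored at the later date, the time between the two counts as time at risk. A death in that interval is unlikely to be recorded, because the site has no contact with the subject.

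Kaplan-Meier multiplies factors of the form 1 − (deaths ÷ number at risk). Subjects who add to the number at risk but have little chance of adding to the deaths make each factor too large. The OS curve is pushed in one direction only, upward. The plan avoids this for subjects alive at cut-off and not for subjects who are lost, so similar people are handled by two rules.

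At stake are the three landmark OS rates. OS is a secondary, descriptive endpoint of a single-arm expansion cohort.

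**Working it through.** No stated figure in the protocol depends on this rule, so there is nothing to reproduce. The check has two parts: the order of the dates, and the size of the effect.

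**1. Order of the dates**

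| Subject | OS censoring date in Table 15 | Relation to last date known alive |
|---|---|---|
| Alive at cut-off | last known alive or last contact | the same date |
| Withdraws consent | withdrawal | the same date, since the subject is alive when withdrawing |
| Lost to follow-up | time of being lost | later, by the contact interval plus the contact attempts (Sections 5.4, 5.5.1) |

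Only the third row is at fault. The contact interval depends on the phase: 12 weeks (±14 days) in OS follow-up (Table 10, note 4), and 3 weeks on treatment (Table 8) and in PFS follow-up (Table 10, note 3).

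**2. Inputs for the size**

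- Contact interval 12 weeks = 84 ÷ 30.4375 = 2.76 months (protocol).
- Contact attempts 0.5 or 1.5 months (assumption). Gap g = 3.26 or 4.26 months.
- Loss to follow-up 5%, 10% or 20% per year, independent of survival (assumption).
- True median OS 9 or 12 months. Section 2.1 says that pre-daratumumab patients refractory to both immunomodulatory agents and PIs "had a median overall survival (OS) ranging from 9 months" to 12 months. Applying this to the present trial, and exponential survival, are assumptions.

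**3. Simulation**

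400,000 subjects per setting, 36-month horizon, 12-week contacts throughout. Each range covers g = 3.26 to 4.26 months.

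| True median | Lost per year | OS at 12 months (true) | 18 months (true) | 24 months (true) |
|---|---|---|---|---|
| 9 months | 5% | 40.2–40.5% (39.7%) | 25.5–25.8% (25.0%) | 16.1–16.4% (15.7%) |
| 9 months | 10% | 40.8–41.3% | 26.2–26.5% | 16.8–17.0% |
| 9 months | 20% | 42.3–42.7% | 27.5–28.1% | 17.8–18.4% |
| 12 months | 5% | 50.5–50.7% (50.0%) | 35.9–36.0% (35.4%) | 25.5–25.7% (25.0%) |
| 12 months | 10% | 51.0–51.4% | 36.3–36.9% | 25.9–26.4% |
| 12 months | 20% | 52.0–52.9% | 37.7–38.5% | 27.3–28.0% |

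The overstatement runs from about 0.5 point (5% per year) to about 3 points (20% per year). Censoring the same simulated subjects at last contact returned the true rates to within about 0.2 point.

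**4. Check by hand**

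With death hazard λ and loss hazard h, the lost-but-still-counted subjects per subject truly at risk settle at r = h(e^((λ+h)g) − 1) ÷ (λ+h), and the estimated hazard is λ ÷ (1 + r). For a true median of 12 months, λ = ln 2 ÷ 12 = 0.05776 per month.

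- 5% per year, g = 3.26: h = −ln(0.95) ÷ 12 = 0.00427; r = 0.00427 × 0.2241 ÷ 0.06203 = 0.0154; hazard 0.05688; OS at 12 months e^(−0.6826) = 50.5%. Simulation: 50.5%.
- 20% per year, g = 4.26: h = −ln(0.80) ÷ 12 = 0.01860; r = 0.01860 × 0.3844 ÷ 0.07636 = 0.0936; hazard 0.05282; OS at 12 months e^(−0.6338) = 53.1%. Simulation: 52.9%.

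The same formula with 3-week contacts (21 ÷ 30.4375 = 0.69 month, so g = 1.19 to 2.19 months) gives about 0.2 to 1.6 points over the same assumed ranges. The table above is therefore the upper case, in which every loss occurs under 12-week contacts.

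**5. Sampling error for comparison**

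With 28 subjects, ignoring censoring, the standard error of a 12-month rate of 50% is √(0.5 × 0.5 ÷ 28) = 9.4 points, and at 39.7% it is √(0.397 × 0.603 ÷ 28) = 9.2 points.

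**The case against.** The strongest reply is that the protocol speaks of the time of being lost and never of a date of declaration. The analysis plan, to which Section 9.8 leaves the complete details, could define that time as the last successful contact. This is possible, and it would remove the problem. But the very next sentence of Table 15 uses last known alive or last contact for a different group, and Section 5.4 makes loss a later determination. The natural reading is the unfavourable one. If last contact is meant, the text should say so.

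Second, some deaths may still be found. Table 10, note 4 has survival documented in medical charts and allows contact by various means. That stands: a death is unlikely to be recorded in the gap, not impossible.

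Third, the effect is minor. That also stands: there is no OS hypothesis, the cohort is small, and the bias is well inside the sampling error.

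A reader might infer more than the documents support:

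- That the whole sentence is wrong. It is not, because a subject withdrawing consent is known to be alive that day.
- That every lost subject gains 12 weeks. That interval applies only in OS follow-up; elsewhere it is 3 weeks.
- That a reported median OS would be inflated. Table 15 promises medians for the endpoints listed before OS; for OS it specifies only the three landmark rates.
- That unreachable subjects are more likely to have died. The protocol gives no basis for this, and changing the censoring date would not cure informative loss.

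**Conclusion.** The point holds as a small correction. As worded, Table 15 censors lost subjects later than the last date they were known alive, unlike subjects alive at cut-off. The bias is always upward. Its size, about 0.5 to 3 percentage points on the 12-, 18- and 24-month OS rates, rests on assumptions that the protocol does not supply: 5% to 20% lost per year under 12-week contacts, 0.5 to 1.5 months of contact attempts, exponential OS with a median of 9 to 12 months, and loss independent of survival. It would be smaller where loss occurs during 3-weekly visits, and absent if nobody is lost. It does not touch the ORR analysis, the sample size or the stopping rules, and ranks at the lowest severity.

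**What to change.** In the OS entry of Table 15, keep censoring at the date of withdrawal for subjects who withdraw consent. Change the rest to state that subjects lost to follow-up are censored at the last known alive or last contact date, by the same derivation as for subjects alive at cut-off. The cost is one sentence. That derivation is already specified in Table 15, so no new data or programming concept is needed.

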## 9.8.2. Safety Analyses

The All Treated Population will be used for the analysis of safety data. All serially collected safety endpoints (e.g. laboratory tests, vital signs, ECGs) will be summarized according to the scheduled, nominal visit at which they were collected and across all on-treatment time points using a “worst-case” analysis. Complete details of the safety analyses will be provided in the RAP.

### 9.8.2.1. Exposure Duration

The number of subjects administered study treatment will be summarized according to the duration of therapy.

### 9.8.2.2. Adverse Events

Adverse events (AEs) will be coded using the standard MedDRA and grouped by system organ class. Adverse events (AEs) will be graded by the investigator according to the National Cancer Institute- Common Toxicity Criteria for Adverse Events (NCI-CTCAE), (version 4.03, [NCI, 2010]). In addition, for belantamab mafodotin treatment related corneal events, the GSK grading scale for corneal events ([Appendix 9](#)) should be used.

Events will be summarized by frequency and proportion of total subjects, by system organ class and preferred term. Separate summaries will be given for all AEs, treatment-related AEs, and SAEs and AEs leading to discontinuation of study treatment. Adverse events (AEs), if listed in the NCI-CTCAE (version 4.03, [NCI, 2010]) will be summarized by the maximum grade. Otherwise, the AEs will be summarized by maximum intensity.

Characteristics (e.g. number of occurrences, action taken, grade, etc) of the following AEs of special interest will be summarized separately:

- Corneal events
- Thrombocytopenia
- Infusion related reactions

The incidence of deaths and the primary cause of death will be summarized.

### 9.8.2.3. Clinical Laboratory Evaluations

Hematology and clinical chemistry data will be summarized using frequencies and proportions according to National Cancer Institute-Common Toxicity Criteria for Adverse Events (NCI-CTCAE) (Version 4.03, [NCI, 2010]). Laboratory test results outside the reference ranges that do not have associated NCI-CTCAE criteria will be summarized using proportions. Further details will be provided in the RAP.

#### **9.8.2.4. Other Safety Measures**

Data for vital signs, ECGs, and ECHOs will be summarized based on predetermined criteria identified to be of potential clinical concern (PCI). Further details will be provided in the RAP.

#### **9.8.3. Pharmacokinetic Analyses**

##### **9.8.3.1. Concentration Time Data**

Linear and semi-logarithmic individual concentration-time profiles and mean and median profiles (when applicable) by belantamab mafodotin dose will be plotted for belantamab mafodotin (ADC and total mAb), cys-mcMMAF, and pembrolizumab (if tested) in Part 1.

Concentrations of belantamab mafodotin (ADC and total mAb), cys-mcMMAF, and pembrolizumab (if tested) will be listed for each subject and summarized (when appropriate) by planned time point and dose cohort in Part 1 and Part 2.

